#### 4.2.2. Main analytical approach

- Frequency and percentage of participants in each category of microbiological response (success/failure) at ToC visit will be summarized along with 95% Clopper-Pearson CI for the primary estimand and these results will be reported by treatment group, and will also be presented graphically.
- Primary estimand will be reported CCI [REDACTED] for the final reporting of the study.
- CCI [REDACTED]  
[REDACTED]  
[REDACTED].
- Details of the planned displays are provided in the OPS.

### 4.3. Secondary Endpoints Analyses

The secondary endpoints to be evaluated are safety and PK.

#### 4.3.1. Pharmacokinetics

Urine and Plasma samples will be used to evaluate PK characteristics of GSK3882347. CCI Final analyses and reporting will be performed by GSK Biostatistics and Programming.

Analysis of pharmacokinetic concentrations will be conducted by using the pharmacokinetic analysis set. Details on the pharmacokinetic estimand are given in Section 1.1.2

Descriptive summaries of plasma and urine concentrations will be presented by cohort. Individual subject level, and aggregate level plots of plasma concentration data will also be presented.

#### 4.3.2. Safety

The following endpoints will be analysed:

- Occurrence of adverse events (AEs) and serious adverse events (SAEs)
- Clinically significant changes from baseline in laboratory values (haematology, chemistry and urinalysis), vital signs and 12-lead electrocardiogram (ECG) readings at each visit

Analysis of safety data will be conducted by using the Safety analysis set. Details on the safety estimand are given in Section 1.1.2. The details of the safety analyses are provided in Section 4.5.

#### 4.4. Exploratory Endpoint(s) Analyses

Efficacy results will be presented on the Micro-MPP analysis set, unless otherwise specified.

CCI

- Clinical resolution response
- Clinical symptom score outcome & response

CCI

A blinded clinical review of concomitant medications will be conducted to determine use of systemic antibacterials.

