### 6.8.3. Rescue Medicine

If participants do not respond clinically (participants experience new, worsening or non-resolving signs and symptoms of uUTI) to randomised medication, they should be given rescue medication. They will be considered a treatment failure and will be provided rescue medication by site as per SoC [Gupta, 2011].

Use of rescue medications is allowable at any time during the study. The requirement for the use of rescue medications should be assessed by the Investigator in accordance with site procedure and treatment guidelines [Gupta, 2011]. If clinically acceptable (and onset of a severe infection is not suspected), rescue medication should be postponed until the next clinical symptom resolution assessment during the On-Therapy period.

Pathogen identification or in vitro resistance of recovered uropathogens alone, is not a reason for study treatment discontinuation through the On-Therapy period. Patients can resolve their infection spontaneously and in the absence of treatment [Little, 2009].

The date and time of rescue medication administration as well as the name and dosage regimen of the rescue medication must be recorded.

Rescue medication to be prescribed by Site Investigator as required and as assessed by the Investigator and in consultation with the Medical Monitor if required by the Investigator. The decision to prescribe rescue medication resides with the Investigator. A combined clinical and laboratory (e.g. serum creatinine and other haematological and biochemical parameters) assessment should be used to prior to withdrawal of study intervention.

The Investigator can request the participant's baseline, enrolling microbiology culture to help in the assessment and additional suitable SoC if required [Gupta, 2011]. Note: The potential for a drug-drug interaction with next line therapy (e.g., trimethoprim-sulfamethoxazole) has been reviewed and is permitted in the study.

If antibiotic rescue medication is given, the participant will complete an early discontinuation visit as per the SoA and will not be required to attend any other subsequent visits.

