### 9.3. Statistical Analyses

#### 9.3.1. General Considerations

The estimands for primary endpoint, Microbiological response rate and secondary endpoints safety and PK are included in Section 3. No formal comparisons against Nitrofurantoin are planned as Nitrofurantoin is included in the study only to ensure unbiased reporting of safety events and analysis was designed to demonstrate that the concept behind the novel mechanism of action of GSK3882347 translates into humans. Clinical outcomes, response rates, CCI form part of the exploratory analysis. Additional exploratory analysis may be conducted on the microbiology samples according to other uropathogen in combination with the qualifying pathogen and CCI to understand the microbiology response rate further depending on the main study results.

In general, data from Cohorts 1 and 2 will be displayed in a single (combined) Table/Figure/Listing; except for selected PK analyses which can only be performed with the full serial time profile.

Microbiological response is the key endpoint used for internal decision-making and additional supportive analyses for internal decision-making may focus on the clinical resolution at the ToC visit, and CCI at ToC and Follow Up visit. CCI

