### 3. ANALYSIS SETS

Analysis Set	Definition / Criteria	Analyses Evaluated
Screened	All participants who signed the ICF and were screened for eligibility.	
 
Study Population
 

Enrolled	
All participants who passed screening and entered the study
 
Note: screening failures [who never passed screening even if rescreened] and participants screened but never enrolled into the study [Met eligibility but not needed] are excluded from the Enrolled analysis set as they did not enter the study.)
	
 
Study Population
 

Randomized	
All participants in the Enrolled analysis set who were randomly assigned to study intervention in the study.
 
Participants will be analyzed according to the intervention they were randomly assigned to.
	
 
Study Population
 

Safety	
All participants in the Randomized analysis set who receive at least 1 dose of study intervention.
 
Participants will be analyzed according to their actual intervention received.
	
 
Safety
 

Microbiological Modified Per Protocol (Micro-MPP)*	
All participants in the Safety analysis set who: receive all planned doses of study intervention; have a Qualifying baseline E. coli from a quantitative bacteriological culture of a pre-treatment clean-catch midstream urine specimen; have completed a ToC visit; have no major protocol deviations that would prevent evaluation of microbiological response.
 
Participants will be analyzed according to their actual intervention received.
	
 
Efficacy
 

CCI

CCI

Analysis Set	Definition / Criteria	Analyses Evaluated
CCI		
Pharmacokinetic (PK)	
All participants in the Safety analysis set who had at least 1 non-missing PK assessment (Non-quantifiable [NQ] values will be considered as non-missing values).
 
Participants will be analyzed according to their actual intervention received.
	
 
Pharmacokinetic
 

CCI		

\*The algorithm for determining qualifying *E. coli* based on microbiology laboratory quantitative culture results is provided in the [Appendix 4](#)

CCI

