#### 4.4.3. Clinical evaluation: Symptoms of uUTI and Clinical Resolution Response

##### ***Definition of endpoints***

##### **Investigator's Assessment of Clinical Resolution Response:**

###### Outcome

- Investigator will examine the participants and will report the clinical resolution response in the eCRF as either resolved or unresolved at each visit.
- Refusal to consent to a clinical examination or failure to attend the visit will have an outcome of indeterminate (clinical resolution failure). This will be determined programmatically.
- At Follow-Up visit outcome will be determined programmatically, as outlined in [Table 1](#).

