###### Response

- No response will be determined for Day 2 through 6 visits.
- Response will be determined programmatically for ToC Visit, where response is a:
  - Clinical resolution success when investigator assessment is “resolved” at ToC

- Clinical resolution failure when investigator assessment is “unresolved” at ToC
- At Follow-Up visit response will be determined programmatically, as outlined in [Table 1](#).

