**Table 1 Clinical Resolution Response (programmatic derivation)**

Defining Criteria for Investigators Assessment of Clinical Symptom Resolution	Outcome	Response
Follow-up Visit		
● Clinically resolved at ToC and Follow-Up visit	Sustained clinical resolution	Clinical resolution success
● Clinically unresolved at ToC visit but clinically resolved at Follow-Up visit	Delayed clinical resolution	Clinical resolution failure
● Clinically resolved at ToC visit but clinically unresolved at Follow-Up visit	Clinical recurrence	Clinical resolution failure
● Clinically unresolved at ToC visit and Follow-Up visit	Clinically unresolved//Clinical worsening	Clinical resolution failure

 
● Refusal to consent to a clinical examination or,
 
● Failure to attend the Follow-Up Visit or, achieved sustained or,
 
● Achieved delayed clinical resolution but received other systemic antibacterials before the Follow-Up visit.
 
	Indeterminate	Clinical resolution failure

ToC=Test of Cure

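### On the visible text, clinical resolution at ToC is summarised in a set that rescued participants normally leave, and its programmed success rule has no antibacterial condition

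*SAP*

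**What the plan says.** **Role.** Clinical resolution is exploratory. Protocol 9.3.1 makes microbiological response the key endpoint for internal decisions and adds that "additional supportive analyses for internal decision-making may focus on the clinical resolution at the ToC visit".

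**Analysis set.** SAP 4.4 states: "Efficacy results will be presented on the Micro-MPP analysis set, unless otherwise specified". Clinical resolution is one of the endpoints listed beneath, and the visible text of SAP 4.4.3 names no other set. Under SAP 3, Micro-MPP members must "receive all planned doses of study intervention; have a Qualifying baseline" *E. coli*, and must also "have completed a ToC visit; have no major protocol deviations that would prevent evaluation of microbiological response".

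**Rescue.** Of participants who do not respond clinically, Protocol 6.8.3 says: "They will be considered a treatment failure and will be provided rescue medication by site as per SoC". After antibiotic rescue they have an early discontinuation visit and need not attend later ones. Protocol 7.1 says the same when study drug is stopped because rescue is needed.

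**Outcome and response rules, SAP 4.4.3.** On missed assessments: "Refusal to consent to a clinical examination or failure to attend the visit will have an outcome of indeterminate (clinical resolution failure"). At ToC: "Clinical resolution success when investigator assessment is" *resolved*, and failure when it is *unresolved*. At Follow-Up, Table 1 makes the outcome indeterminate, hence a failure, for a participant who "Achieved delayed clinical resolution but received other systemic antibacterials before the Follow-Up visit". The same row covers sustained resolution.

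**Definition.** Protocol 8.1.1 makes having no need for another antimicrobial part of the investigator's judgement of clinical resolution. SAP 4.4 plans a blinded review of concomitant medication to identify systemic antibacterial use, but does not say how its result enters the ToC clinical rule.

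**The concern.** Poor symptomatic response leads to rescue, rescue ends required attendance, and attendance is a condition of the analysis set. Membership of the set therefore depends partly on the outcome it is used to measure. The completer focus is argued in Protocol 3 and SAP 1.1.1 for the microbiological estimand. No visible text argues it for a symptom endpoint that can itself cause a participant to stop.

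The second gap is smaller. The SAP programs an antibacterial check at Follow-Up but not at ToC, the visit that Protocol 9.3.1 mentions for possible decision support. At stake is a clinical rate that looks better than the experience of the treated, culture-positive participants and is read as corroborating the primary result.

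**Working it through.** The plan gives no expected clinical resolution rate and no expected rescue rate, so there is no planned figure to reproduce. The first two steps compare the texts; the third illustrates size.

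**Step 1: who is in the set at ToC.** Take a dosed participant with qualifying *E. coli*.

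- Rescued during dosing, study drug stopped: not all planned doses, so outside Micro-MPP. SAP Table 2 agrees: it says that in the primary estimand's population rescue could occur only after the 5-day dosing period.
- Full dosing, rescued before ToC, does not attend ToC: no completed ToC visit, so outside Micro-MPP.
- Full dosing, rescued before ToC, attends ToC: inside. She is a microbiological failure under SAP 1.1.1. Her clinical response is whatever the investigator marks.
- Full dosing, no rescue, attends ToC *unresolved*: inside, and a clinical failure.

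The first two groups are treatment failures under Protocol 6.8.3 but are not in the denominator. The SAP's non-attendance rule would make them clinical failures, but in a set that requires a completed ToC visit it has nobody to act on at ToC.

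**Step 2: the ToC rule against the Follow-Up rule.** The Protocol 8.1.1 definition governs the investigator's judgement at both visits. At Follow-Up the SAP adds a programmed antibacterial check; at ToC it does not. In the third case above, if the investigator marks *resolved*, the participant is a clinical success and a microbiological failure at the same visit.

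**Step 3: size.** Inputs: n = 21, the approximate evaluable target for the GSK3882347 arm in the protocol synopsis, taken here as the Micro-MPP size (assumption). The number resolved, x, is assumed to be 10, 13 or 16. The number of clinical failures outside the set, k, is assumed to be 0 to 6. Displayed rate = x/21; rate with dropped failures counted = x/(21 + k).

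| Resolved x | k = 0 | k = 2 | k = 4 | k = 6 |
|---|---|---|---|---|
| 10 | 47.6% | 43.5% | 40.0% | 37.0% |
| 13 | 61.9% | 56.5% | 52.0% | 48.1% |
| 16 | 76.2% | 69.6% | 64.0% | 59.3% |

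For x = 13 the 95% Clopper-Pearson intervals run from 38.4–81.9% (13/21) through 34.5–76.8% (13/23) and 31.3–72.2% (13/25) to 28.7–68.1% (13/27). The displayed rate is higher by 61.9 − 56.5 = 5.4 to 61.9 − 48.1 = 13.8 points. Over the whole table the difference runs from 47.6 − 43.5 = 4.1 to 76.2 − 59.3 = 16.9 points.

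Recoding one *resolved* participant already among the 21 as a failure for antibacterial use lowers the rate by 1/21 = 4.8 points, for example from 13/21 = 61.9% to 12/21 = 57.1%.

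**The case against.** Redaction is the strongest answer. Blocks immediately before and after the endpoint list in SAP 4.4 are blacked out, as are analysis-set rows after Micro-MPP in SAP 3. SAP 4.4.6 and Appendix 4 show a redacted set beside Micro-MPP, and SAP Table 2 describes a Micro-MITT set of participants with at least one dose and a qualifying *E. coli*. A reader might infer that clinical resolution is analysed *only* in completers. The documents neither show nor exclude that. The non-attendance rule is also written for visits in general and would work at ToC in a Micro-MITT-type set. This limits the population point to the visible text.

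Second, a reader might infer that the ToC rule ignores rescue antibacterials. It does not: Protocol 8.1.1 puts that condition inside the judgement the rule uses. A false success needs full dosing, rescue before ToC, attendance that was not required, and a *resolved* mark despite the definition. What stands is that the program does not enforce the condition at ToC, although the SAP thought enforcement worthwhile at Follow-Up under the same definition.

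Third, not all clinical failures are lost. Those *unresolved* at an attended ToC visit remain as failures if they meet the other Micro-MPP conditions. Discontinuations with reasons, deviations leading to exclusion, and rescue medication are summarised under SAP Appendix 1. That makes the losses visible, but it does not put them into the clinical rate.

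Finally, Protocol 9.3.1 says only that decision analyses *may* look at this endpoint, no hypothesis is tested, and Protocol 4.2 disclaims firm efficacy conclusions. All of that stands and sets the scale of the point.

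**Conclusion.** The point holds in limited form. On the visible text, the default set for ToC clinical resolution normally omits participants rescued or stopped for clinical failure, and the programmed ToC response does not enforce the antimicrobial part of the protocol's definition. Both push an exploratory descriptive rate upward; neither affects an error rate.

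The 4 to 17 point range rests on assumed counts: 21 in the set, 10 to 16 resolved, 2 to 6 failures outside it. The documents give no rescue rate. The 4.8 points apply only to someone already counted among the 21. A reader might add about 5 points for every rescued participant who returns resolved. If she is additional to the 21, she enters numerator and denominator, and 13/21 = 61.9% becomes 14/22 = 63.6%, a rise of 1.7 points.

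A reader might also extend the point to the symptom-score response. The algorithms in SAP Appendix 7 are not visible, so nothing can be concluded about whether they already handle rescue.

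**What to change.** 1. In SAP 4.4.3, define clinical resolution success at ToC as an investigator assessment of *resolved* and no other systemic antibacterial before ToC. Take antibacterial use from the blinded review already planned in SAP 4.4. This aligns ToC with Table 1.

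2. Keep the Micro-MPP summary. Beside it, report ToC clinical resolution in all dosed participants with qualifying baseline *E. coli*, using the Micro-MITT definition in SAP Table 2, with rescue before ToC or non-attendance at ToC counted as failure. If redacted text already provides this, the sponsor need only confirm it.

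Leave the symptom-score algorithm unchanged on this account.

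The cost is SAP wording, one further population in existing tables, and a possibly less favourable clinical rate. The wider-set figure is conservative for anyone who misses ToC for reasons unrelated to symptoms, but that follows the SAP's own rule for missed visits.

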##### 4.4.1. PK Parameters

PK parameters will be calculated by standard non-compartmental methods.

The definition of the PK parameters of interest are given in the table below.

Parameter	Parameter Description	Cohort	Type
CCI			
C22-24,U	Concentration of GSK3882347 in urine during the 22-24 h collection interval	Combined cohorts, Day 1, 2, 3, 4, 5	Urine

CCI

CCI

#### 4.4.2. Microbiological Outcome and Response

##### ***Definition of endpoints/estimands***

The microbiological outcome is determined by comparing the baseline culture results to the culture results at each subsequent visit by using a prespecified programmed algorithm for each participant, considering the number of baseline qualifying uropathogens. The algorithm for determining qualifying *E. coli* is provided in the [Appendix 4](#) and the detailed definitions for outcome and response are provided in Appendix 6.

The estimand for microbiological outcome and response is detailed in Section [1.1.1](#).

##### ***Main analytical approach***

- Frequency and percentage of participants in each category of microbiological outcome at CCI [REDACTED] ToC CCI [REDACTED] will be summarized along with 95% Clopper-Pearson CI by treatment group.
- Results will also be presented graphically over time and by treatment group.
- CCI [REDACTED]
- An exploratory statistical analysis to model the number of responders, adjusting for known covariates (e.g. age, history of UTIs) may be produced.
- CCI [REDACTED].

#### 4.4.3. Clinical evaluation: Symptoms of uUTI and Clinical Resolution Response

##### ***Definition of endpoints***

##### **Investigator's Assessment of Clinical Resolution Response:**

###### Outcome

- Investigator will examine the participants and will report the clinical resolution response in the eCRF as either resolved or unresolved at each visit.
- Refusal to consent to a clinical examination or failure to attend the visit will have an outcome of indeterminate (clinical resolution failure). This will be determined programmatically.
- At Follow-Up visit outcome will be determined programmatically, as outlined in [Table 1](#).

###### Response

- No response will be determined for Day 2 through 6 visits.
- Response will be determined programmatically for ToC Visit, where response is a:
  - Clinical resolution success when investigator assessment is “resolved” at ToC

- Clinical resolution failure when investigator assessment is “unresolved” at ToC
- At Follow-Up visit response will be determined programmatically, as outlined in [Table 1](#).

**Table 1 Clinical Resolution Response (programmatic derivation)**

Defining Criteria for Investigators Assessment of Clinical Symptom Resolution	Outcome	Response
Follow-up Visit		
● Clinically resolved at ToC and Follow-Up visit	Sustained clinical resolution	Clinical resolution success
● Clinically unresolved at ToC visit but clinically resolved at Follow-Up visit	Delayed clinical resolution	Clinical resolution failure
● Clinically resolved at ToC visit but clinically unresolved at Follow-Up visit	Clinical recurrence	Clinical resolution failure
● Clinically unresolved at ToC visit and Follow-Up visit	Clinically unresolved//Clinical worsening	Clinical resolution failure

 
● Refusal to consent to a clinical examination or,
 
● Failure to attend the Follow-Up Visit or, achieved sustained or,
 
● Achieved delayed clinical resolution but received other systemic antibacterials before the Follow-Up visit.
 
	Indeterminate	Clinical resolution failure

ToC=Test of Cure

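### SAP Table 1 codes many antibiotic-treated relapses after ToC as 'Indeterminate', so the exploratory recurrence count at Follow-up is biased low and mixed with missing visits

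*SAP*

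**What the plan says.** SAP 4.4.3, Table 1, derives the Follow-up outcome from the investigator's resolved/unresolved assessments at ToC and Follow-up. *Clinical recurrence* has one defining criterion: "Clinically resolved at ToC visit but clinically unresolved at Follow-Up visit". The *Indeterminate* row includes "Failure to attend the Follow-Up Visit". It also covers resolution recorded after antibacterials; the last part reads "Achieved delayed clinical resolution but received other systemic antibacterials before the Follow-Up visit". The bullets in that row are broken across lines ("Failure to attend the Follow-Up Visit or, achieved sustained or"), and I read them as sustained or delayed resolution with other systemic antibacterials before Follow-up. The SAP text above the table also makes non-attendance indeterminate. Both *Clinical recurrence* and *Indeterminate* map to clinical resolution failure. The main analytical approach in SAP 4.4.3 reports each outcome category, as well as the response, with a 95% Clopper-Pearson interval by treatment group.

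Protocol 6.8.3 says of participants with new, worsening or non-resolving signs and symptoms that "they should be given rescue medication". On timing it says: "Use of rescue medications is allowable at any time during the study". Once antibiotic rescue is given, "the participant will complete an early discontinuation visit as per the SoA and will not be required to attend any other subsequent visits".

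Both schedules of activities (Protocol 1.3.1 and 1.3.2) mark the investigator's resolution assessment, the symptom score and a urine microbiology sample in the early discontinuation column. Table 1 has no rule that uses any of them, and SAP 6.3.4 does not map that visit to Follow-up.

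**The concern.** The protocol's rescue pathway and the SAP's coding rule work against each other. The event that Table 1 is meant to count, a return of symptoms after resolution at ToC, leads to treatment and releases the participant from the one visit at which Table 1 can record it. The information that would identify her is scheduled for collection at the early discontinuation visit but has no place in the derivation.

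The exploratory objective is resolution of symptoms over time through Follow-up, and Protocol 8.1.1 names ToC and Follow-up as the key timings. For a drug that blocks bacterial attachment, return of symptoms after dosing stops is a natural question. A recurrence percentage that leaves out part of the treated relapses does not answer it. An *Indeterminate* percentage that mixes treated relapse with refusal and unexplained absence cannot be interpreted as missing data either.

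**Working it through.** **Tracing the rule.** Take a participant in the Micro-MPP set, which requires a completed ToC visit, who is resolved at ToC and relapses before Follow-up.

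| What happens next | Table 1 outcome | Response |
|---|---|---|
| Treated, does not attend Follow-up | Indeterminate | Failure |
| Treated, attends, recorded resolved | Indeterminate | Failure |
| Treated, attends, recorded unresolved | Clinical recurrence | Failure |
| Untreated, attends, still unresolved | Clinical recurrence | Failure |
| Relapse first found at Follow-up | Clinical recurrence | Failure |

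The first two rows are where recurrences are lost. The last column shows that the response does not depend on which label is used.

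**Size.** The plan states no recurrence figure, so there is nothing to reproduce. What follows is an illustration.

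Inputs from the documents:
- ToC is Day 10 to 13 and Follow-up is 28±3 days after the first dose, taken as Days 25 to 31. The gap W runs from 25 − 13 = 12 to 31 − 10 = 21 days.
- About 21 evaluable participants on GSK3882347 (Protocol 1.1).

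Assumptions, none given in the documents:
- onset is uniform over W;
- delay d from onset to antibacterial is 1 to 5 days;
- a share t of recurrences is treated;
- a share u of those treated before Follow-up attend it and are recorded unresolved;
- untreated recurrences are still present at an attended Follow-up, which favours the current rule.

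Share of recurrences coded as such = 1 − t(1 − d/W)(1 − u).

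With t = 1 and u = 0 this reduces to d/W:
- d = 1: 1/21 = 4.8% to 1/12 = 8.3%
- d = 3: 3/21 = 14% to 3/12 = 25%
- d = 5: 5/21 = 24% to 5/12 = 42%

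Other settings, lowest (d = 1, W = 21) to highest (d = 5, W = 12):
- t = 0.9, u = 0: 1 − 0.9 × 20/21 = 14% to 1 − 0.9 × 7/12 = 47.5%
- t = 0.7, u = 0: 1 − 0.7 × 20/21 = 33% to 1 − 0.7 × 7/12 = 59%
- u = 0.2, t from 0.7 to 1: 1 − 1 × (20/21) × 0.8 = 24% to 1 − 0.7 × (7/12) × 0.8 = 67%

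**In counts.** Treat all 21 as resolved at ToC and use the t = 1, u = 0 range. With true recurrence R and captured share s, expected coded recurrences = 21Rs and P(none coded) = (1 − Rs)^21.
- R = 20% (4.2 true): 4.2/21 = 0.2 to 4.2 × 5/12 = 1.75 coded; P(none coded) 82% to 16%.
- R = 40% (8.4 true): 8.4/21 = 0.4 to 8.4 × 5/12 = 3.5 coded; P(none coded) 67% to 2%.

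The count is too low in every setting tried. How far too low depends entirely on t, d and u.

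**The case against.** The strongest reply is that the label does little work. Every *Indeterminate* case is a response failure, the endpoint is exploratory, the study tests no hypotheses, and about 21 evaluable participants are planned on drug. Rescue medication is summarised with concomitant medications and withdrawal reasons are tabulated (SAP 6.1.4 and 6.1.1), so treated relapses are not invisible. All of this stands and limits the importance of the point. It does not make the recurrence row or its interval right.

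Second, Protocol 8.1.1 defines clinical resolution as including no need for other antimicrobial therapy. A treated participant who attends Follow-up may therefore be recorded unresolved and reach the recurrence row. Later visits are not required, but they are not barred, and the decision to prescribe rests with the investigator. This also stands: not every treated relapse is lost. However, the antibacterial clause in Table 1 itself presupposes treated participants recorded as resolved, and those who do not return remain *Indeterminate*.

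Third, parts of the plan are not visible. The symptom-score rules in Appendix 7 are not shown, several SAP 4.4 sections are redacted, and data-handling detail is deferred to the OPS. The point is therefore confined to Table 1 as written.

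A reader might infer that the recurrence category will be nearly empty however often infection returns. The documents do not support that. They give no rates or delays, the coded count rises with the true rate, and near-emptiness needs almost universal treatment within about a day with almost no treated participant attending unresolved. A reader might also infer that the table would look like durable benefit. It would not: sustained resolution is the only success row, and no treated relapse that follows the paths above can enter it as a success.

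**Conclusion.** The point holds for one category of an exploratory outcome table. As written, Table 1 omits from *Clinical recurrence* those post-ToC relapses that are treated and either do not return or return recorded as resolved, and it places them with missing visits. The recurrence percentage and its Clopper-Pearson interval are therefore biased low.

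The captured share is about 5% to 42% if all recurrences are treated 1 to 5 days after onset and none of the treated attend unresolved. It is 33% to 59% if 70% are treated, and up to 67% in the most favourable setting tried. These ranges illustrate assumptions and are not estimates for this trial. Success/failure at Follow-up, the ToC clinical result and the primary microbiological endpoint do not change. The recoding is worth making before unblinding because it is cheap and the key assessment is already scheduled.

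**What to change.** Change analysis coding only, in SAP Table 1:

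1. Code *Clinical recurrence* (or a separate category, *recurrence, treated*) for any participant resolved at ToC who is then assessed unresolved at a post-ToC early discontinuation visit or at Follow-up, or who receives a systemic antibacterial for uUTI before Follow-up.
2. State the order of precedence among rows. Under the new rule a treated relapse who misses Follow-up meets both the recurrence and non-attendance criteria. Already, resolution after antibacterials meets both a resolution row and the *Indeterminate* row.
3. Keep *Indeterminate* for assessments missing without rescue and for antibacterials given for another indication.
4. Extend the blinded concomitant-medication review in SAP 4.4 to classify indication. As written it determines only the use of systemic antibacterials, and Protocol 6.8.3 requires the date, time, name and regimen of rescue to be recorded but does not mention indication.

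Within the illustration above, this captures every recurrence by construction. In practice, an untreated relapse with no later assessment would remain *Indeterminate*. The response column is unchanged. The cost is minor programming, a small extension of the review, and a recurrence count that will look less favourable.
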